In theory, patients with Eustachian tube dysfunction as defined by negative pressure on tympanometry will have more resistance in the Eustachian tube. Thus, the pressure required to open should be higher than the pressure in patients with normal function. This relationship has never been evaluated. It would have an impact not only when considering CPAP as a treatment modality, but also when considering CPAP in post-operative patients undergoing otologic surgery. We hypothesize an inverse relationship between middle ear pressure and air pressure as delivered by CPAP required to create both subjective (“popping” the ears) and objective (tympanometric and otoscopic) increase in middle ear pressure. We will begin recruiting participants from clinic and the general population. Each individual participant will be assigned a participant ID. The participant will be brought to the exam room and fitted with a new CPAP mask. Photodocumentation of otoscopic examination will be obtained for baseline as well as tympanometric measurement. Starting at a set pressure, the patient will be given a set number of breaths. Then, the setting will be increased until a maximum tolerable pressure is reached (no higher than 20 cm H₂O). The participant will be asked to notify the examiner when he or she has a sensation of his ears “popping”, and that level will be documented. Photodocumentation and tympanometric measurement will be obtained. These will be used to plot correlation between opening pressure and both initial middle ear pressure as observed on tympanometry and otoscopic evaluations. The Sade classification scheme will be used to grade otoscopic findings. These findings will be analyzed using SPSS and tests include Spearman correlations, t-tests, and Wilcoxon Rank-Sum Test.

Background

1. Provide the scientific background, rationale and relevance of this project.

Eustachian tube dysfunction and chronic otitis media

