Treatment of ETD has also been elusive. While many methods have been proposed, including but not limited to devices such as the Otovent (Kestrel Medical, United Kingdom), surgical interventions such as balloon dilation, myringotomy with ventilation tube placement, laser coagulation, and others, none has provided sufficient data to prove a long-term benefit of the stated intervention. The value of preventing progression of chronic otitis media and its sequelae – including cholesteatoma, hearing loss, severe infections, and need for repeated surgical interventions – is unquestioned.

Continuous positive air pressure therapy

Continuous positive air pressure therapy (CPAP) is a highly successful treatment of an increasingly common problem – obstructive sleep apnea (OSA). Patients using CPAP for OSA have been evaluated in regard to middle ear function. Common otologic complaints related to CPAP include aural fullness and the development of serous otitis media. On the whole, CPAP use is quite safe for the middle ear, although rare case reports have suggested association with negative side effects including a single report of perilymph fistula formation. The most likely mechanism by which the ears are affected by CPAP is that air is forced into the Eustachian tube. Multiple studies have found higher middle ear pressures with CPAP use, although in patients without ETD, the middle ear pressure is likely to revert to a normal pressure. The impact of CPAP on the middle ear still has significant room for investigation.

Hypothesis to be Tested

There is a specific CPAP pressure at which individuals’ Eustachian tubes will allow air to be transmitted to middle ear. We will be able to correlate this to initial middle ear pressure.

Primary outcome measure: CPAP pressure required for middle ear insufflation.

Secondary outcome measures:

- Change in middle ear pressure with CPAP use
- Otoscopic findings
- Patient symptom survey (ETDQ-7)

Study Design: Biomedical

1. Will controls be used? No
2. What is the study design? Cohort study
3. Does the study involve a placebo? No

Human Participants

Ages: 18-99

Sex: M or F

Race: Any

Subjects- see below

1. **Provide target # of subjects (at all sites) needed to complete protocol.** 29
2. **Describe expected rate of screen failure/ dropouts/withdrawals from all sites.** 5%
3. **How many subjects will be enrolled at all sites?** 31
4. **How many subjects will sign a consent form under this UVa protocol?** 31

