5. **Provide an estimated time line for the study.**

After IRB approval, we anticipate completion of enrollment and study completion within 2 months. Data analysis will be concluded within 6 months of study initiation. No follow up is required.

Inclusion/Exclusion Criteria

1. List the criteria for inclusion

- Age \geq 18
- No use of CPAP within past 30 days
- Individuals presenting to the UVA otolaryngology clinic who are otherwise healthy

2. List the criteria for exclusion

- Pre-existing cardiopulmonary disease that presents a risk with CPAP use
- Inability to tolerate CPAP
- Recent otologic surgery

3. List any restrictions on use of other drugs or treatments. None

Statistical Considerations

1. Is stratification/randomization involved?

As there will be no comparison group, there will not be stratification or randomization. Any grouping will be performed in the data analysis portion based on data acquired within the study.

2. What are the statistical considerations for the protocol?

Primary endpoint:

- CPAP pressure at which a significant change in middle ear pressure occurs

Secondary endpoints:

- Tympanometry
- Otoscopy
- ETDQ-7

3. Provide a justification for the sample size used in this protocol.

We anticipate accruing 5-10 participants per week. The accrual goal will be 32, with an interim analysis at 16. We anticipate a very low dropout rate, but will account for a 5% rate. Based on calculations assuming a -0.500 correlation between “opening pressure” (CPAP pressure) and starting middle ear pressure, 29 participants are needed to show statistically significant differences. There is no required follow up, so this provides minimal drop-out risk.

4. What is your plan for primary variable analysis?

We will perform Spearman correlation calculations to estimate the relationship of CPAP pressure at which the ears “pop” to the initial and final tympanometric pressure as well as the change in tympanometric pressure.

5. What is your plan for secondary variable analysis?

We will use t-tests and/or ANOVA to assess the relationship of the above pressures to ETDQ-7 responses as well as using ROC curve analyses to determine if there is a true tympanometric pressure cut point to define ETD.

6. Have you been working with a statistician in designing this protocol? No

7. Will data from multiple sites be combined during analysis? No

Biomedical Research

1. What will be done in this protocol?

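### Item 4 makes three linked correlations the primary analysis, although the hypothesis and the sample size of 29 concern initial pressure only

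*Combined protocol and SAP*

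**What the plan says.** Four places bear on which correlation is primary.

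- **Hypothesis.** The section Hypothesis to be Tested posits an opening CPAP pressure and continues: "We will be able to correlate this to initial middle ear pressure". The summary at the start of the protocol gives the direction: "We hypothesize an inverse relationship between middle ear pressure and air pressure as delivered by CPAP".
- **Sample size** (Statistical Considerations, item 3). The calculation assumes a correlation of -0.500 between opening pressure and starting middle ear pressure, and concludes that "29 participants are needed to show statistically significant differences". The same item says: "The accrual goal will be 32, with an interim analysis at 16".
- **Outcome lists.** The secondary outcome measures include "Change in middle ear pressure with CPAP use". Item 2 also lists tympanometry as a secondary endpoint.
- **Primary analysis** (item 4). Spearman correlations are to estimate how the popping pressure relates "to the initial and final tympanometric pressure as well as the change in tympanometric pressure".

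Item 2 gives the primary endpoint as "CPAP pressure at which a significant change in middle ear pressure occurs". There the pressure change defines the opening pressure. It does not say what the opening pressure is to be correlated with. The plan states no alpha, no order among the three correlations and no rule for combining them.

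**The concern.** Item 4 is the operative analysis text, and it gives primary status to two correlations for which the study has neither a hypothesis nor a sample size. Change is primary in item 4 and secondary in the outcome list.

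Suppose the correlation with initial pressure were unremarkable but the one with final pressure or with change reached significance. Item 4 would then allow that result to be reported as a primary finding. The risk is a conclusion chosen after the data are seen, in a small single-site study with no comparison group. Participants' care is not affected.

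**Working it through.** **1. The plan's own figure.** Item 3 gives r = -0.500 and n = 29. It gives no alpha, sidedness or power. Fisher's z with an assumed two-sided 5% and 80% power:

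n = ((1.960 + 0.842) / atanh(0.5))² + 3, with atanh(0.5) = 0.5493, gives 29.01.

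This matches 29. One-sided 5% at 80% power would give 23.5, and two-sided 5% at 90% would give 37.8. Two-sided 5% is therefore a reasonable working assumption for the level of each test, and 29 corresponds to one test.

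**2. Three tests instead of one.** Three independent tests at 5% would give 1 - 0.95³ = 14.3%. These three are not independent, because they share the popping pressure and change = final - initial. The result depends on the correlation between initial and final pressure (rho) and on the ratio k = SD(final)/SD(initial). The documents give neither, so both are assumed over a range.

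Null trials were simulated with popping pressure unrelated to either reading, continuous normal data, n = 29, three Spearman tests at two-sided 5%, and 60,000 trials per setting. Chance of at least one significant result:

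| k | rho 0 | 0.5 | 0.7 | 0.9 | 0.95 | 0.99 |
|---|---|---|---|---|---|---|
| 0.5 | 11.7% | 11.7% | 11.1% | 9.4% | 8.4% | 6.8% |
| 1 | 11.9% | 12.6% | 12.8% | 11.8% | 11.4% | 11.0% |
| 2 | 11.7% | 11.7% | 11.1% | 9.2% | 8.5% | 6.8% |

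A separate set of 40,000 trials per setting at n = 29, 31 and 32 gave 9.2-12.9% for rho 0-0.9, and 6.6-8.5% for rho 0.95-0.99 with k = 0.5 or 2. The test of initial pressure alone gave 4.8-5.2%.

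**3. The selective-reporting part.** In the same trials, final or change was significant while initial was not in 4.1-7.7% for rho 0-0.9. This agrees with the difference between any-of-three and initial alone: at k = 2, rho = 0.9 it is 9.2 - 4.9 = 4.3 points, and at k = 1, rho = 0.7 it is 12.8 - 5.2 = 7.6 points.

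**4. Change is not separate evidence.** Suppose popping pressure correlates -0.5 with initial pressure, as item 3 assumes, and final pressure has no link to it beyond initial pressure. Then

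corr(pop, change) = 0.5 (1 - rho·k) / sqrt(1 + k² - 2·rho·k).

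- k = 0.5, rho = 0.97: 0.5 × 0.515 / sqrt(0.28) = +0.49
- k = 1, rho = 0.5: 0.5 × 0.5 / sqrt(1) = +0.25
- k = 2, rho = 0.5: 0
- k = 2, rho = 0.97: 0.5 × (-0.94) / sqrt(1.12) = -0.44

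A clear correlation with change, of either sign, can thus arise from the baseline relationship alone.

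**The case against.** The strongest reply is that the intent is already plain. The hypothesis names initial pressure, the sample size uses starting pressure, and change and tympanometry are secondary. The opening summary speaks of plotting opening pressure against initial middle ear pressure and otoscopic findings; final pressure and change do not appear there. On this view, item 4 is one over-inclusive sentence. That largely stands: a reader might infer that the deciding comparison cannot be identified, and the documents do not support so strong a claim. What remains is that item 4, the text an analyst would follow, contradicts the other sections.

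The second reply is that 9-13% belongs to a decision rule the plan never states. Item 4 speaks of estimating, no alpha is given, and item 3's reference to significance follows from the calculation on starting pressure only. This also stands. The figure is conditional, and it should not be read as the error rate of the plan as written.

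Third, the inputs are assumed, and the data will not be smooth. Pressure is raised in settings up to 20 cm H₂O, and no value is defined for a participant who never reports a pop. The range is illustrative.

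A reader might also add the interim at 16 and infer a larger inflation. If all three correlations could support a claim at both looks, the simulated chance is 15.4-20.8% for rho 0-0.9. The documents plan no such use: the interim has no stated purpose, and the stopping and decision rules mentioned in the Data and Safety Monitoring Plan (5.3) are an entry in a general review list, with none defined. That figure is not part of this point.

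**Conclusion.** The point holds as an internal contradiction: three correlations are primary in item 4, against one in the hypothesis and the sample size, with change classified both ways. It should be fixed.

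If each correlation were tested at two-sided 5% at the final analysis and any significant one were reported as primary, the false-positive chance would be about 9-13% instead of about 5%. It would be about 7-8.5% if initial and final readings were nearly collinear with unequal SDs. This rests on an assumed alpha, an assumed any-one-counts rule, and an assumed correlation and SD ratio. The contradiction itself rests on none of these.

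The differing definitions of opening pressure are a separate matter: an objective pressure change or insufflation in item 2 and in "Primary outcome measure: CPAP pressure required for middle ear insufflation", against the popping sensation in item 4. They need to be reconciled in their own right.

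**What to change.** Align item 4 with the hypothesis and item 3, for example:

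*The single primary test is the Spearman correlation of opening pressure with initial tympanometric pressure, two-sided 0.05, at the final analysis. Correlations with final pressure and with change in pressure are secondary. The interim analysis at 16 involves no hypothesis test.*

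If a test at 16 is in fact intended, its boundary has to be stated instead. The term opening pressure in this sentence should follow whatever definition the sponsor settles on.

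The cost is wording only: nothing new is collected, and the calculation behind 29 is unchanged. The downside is that final pressure and change lose primary status. Keeping all three as primary under a Bonferroni correction (0.05/3 = 0.0167 each) would cost more. By the same Fisher formula, r = -0.5 would need 37.7, so 38 evaluable participants, and power at 29 would fall from about 80% to about 66%.

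### The planned correlation of opening pressure with raw change in tympanometric pressure can restate the hypothesised baseline correlation, and no analysis adjusts for initial pressure

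*Combined protocol and SAP*

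**What the plan says.** Item 4 of Statistical Considerations plans Spearman correlations of the CPAP pressure at which the ears pop "to the initial and final tympanometric pressure as well as the change in tympanometric pressure". That makes three correlations, all under the primary variable analysis. Change is not defined further, and I read it as final minus initial pressure. No partial correlation, regression on initial pressure or other adjustment appears anywhere in the document.

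The hypothesis concerns initial pressure only. The opening summary says "We hypothesize an inverse relationship between middle ear pressure and air pressure as delivered by CPAP", and the section Hypothesis to be Tested says "We will be able to correlate this to initial middle ear pressure". The sample size in item 3 rests on that same pair: "Based on calculations assuming a -0.500 correlation between" opening pressure and starting middle ear pressure, from which "29 participants are needed to show statistically significant differences".

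The section Hypothesis to be Tested lists "Change in middle ear pressure with CPAP use" as a secondary outcome, whereas item 4 places its correlation in the primary analysis.

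**The concern.** Initial pressure is one of the two components of the change score. If opening pressure is inversely related to initial pressure, as the study expects, subtracting initial pressure pushes the correlation with change in the positive direction. This happens even if opening pressure says nothing about final pressure once initial pressure is known.

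A study that confirms its hypothesis could then also report that participants who needed more CPAP had a larger rise in middle ear pressure, and present this as an additional result. It may be no more than the initial-pressure correlation over again. This matters because the Risk/Benefit Analysis looks ahead to CPAP as a treatment for Eustachian tube dysfunction and to advice after ear surgery, and there is no control group against which to check the reading.

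**Working it through.** **Inputs from the document.** Correlation of opening with initial pressure, ρ = -0.5 (item 3). Sample size 29 (item 3). Spearman tests (item 4).

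**Inputs assumed.** Two-sided 5% and 80% power, which are not stated but reproduce the plan's 29. The ratio k = SD of final / SD of initial pressure and the correlation r of final with initial pressure are also not given. The only hint is qualitative: the Background expects pressure to return to normal in people without Eustachian tube dysfunction, which suggests a slope below 1 but supplies no figure.

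**Step 1: the plan's own figure.** By Fisher's z, N = ((1.960 + 0.842) / atanh(0.5))² + 3 = (2.802 / 0.5493)² + 3 = 29.01. The stated 29 is reproduced. It concerns initial pressure only.

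**Step 2: the induced correlation.** Scale initial pressure to SD 1. With no link of opening pressure to final pressure given initial pressure, the correlation of opening with final pressure is ρr. Then

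- covariance of opening pressure (SD 1) with change = ρrk - ρ = -ρ(1 - kr)
- variance of change = 1 + k² - 2kr
- correlation with change = -ρ(1 - kr) / √(1 + k² - 2kr)

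The product kr is the slope of final on initial pressure. Example with k = 1, r = 0: 0.5 / √2 = 0.354. Example with k = 1, r = 0.7: 0.5 × 0.3 / √0.6 = 0.194.

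**Step 3: how often each test gives p < 0.05.** Trivariate normal data, n = 29, ρ = -0.5, no link given initial pressure.

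| k | r | Induced correlation | Raw change, p < 0.05 | Partial Spearman, p < 0.05 |
|---|---|---|---|---|
| 0.25 | 0 | +0.485 | 72% | 5% |
| 0.25 | 0.9 | +0.495 | 75% | 6% |
| 0.5 | 0 | +0.447 | 64% | 5% |
| 0.5 | 0.5 | +0.433 | 61% | 5% |
| 1 | 0 | +0.354 | 43% | 5% |
| 1 | 0.5 | +0.250 | 23% | 5% |
| 1 | 0.7 | +0.194 | 15% | about 5% |
| 1 | 0.9 | +0.112 | 9% | 6% |
| 1.25 | 0.8 | 0 | 5% | 5% |
| 2 | 0.75 | -0.177 | 14% | 6% |

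The partial test is the correlation of opening with final pressure given initial pressure. In the last two rows the slope is 1 and 1.5: the excess disappears at slope 1 and the sign reverses above it. With 31 or 32 participants the k = 1, r = 0 row becomes 46% or 47%.

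**Step 4: the boundary.** With ρ = 0 the raw-change test rejects in about 5% of studies in every setting run. The excess comes from the hypothesised baseline relation and not from subtraction alone.

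**The case against.** Several points on the other side stand.

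- **It is a true association.** Opening pressure is measured separately and is not part of the change score. In the settings above, the population correlation with change really is non-zero: people who start lower and need more pressure do move further. Choosing the marginal or the conditional association is a choice of question. What remains is that the marginal one is not independent of the initial-pressure result.
- **The main result is untouched.** The hypothesis and the 29 concern initial pressure, and change is elsewhere listed as secondary.
- **Final pressure is also correlated with opening pressure.** If final pressure is unrelated to initial pressure, that correlation is expected to be zero and would show that the change result reflects baseline. The cross-check fails as r grows. With no link given initial pressure, the correlation with final pressure is itself significant in 24% of studies at r = 0.5 and 48% at r = 0.75, through initial pressure alone.
- **The adjusted test is not flawless.** It assumes that initial pressure is measured without error. With equal SDs, r = 0.7 and opening and final pressure linked only through true initial pressure, partial Spearman rejects in 12% of studies at an assumed reliability of 0.8 (raw change 7%) and 24% at 0.7 (raw change 5%). If final is unrelated to initial pressure it stays at 5%. The documents give no reliability figure.

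A reader might infer that the baseline relation is bound to produce a significant change result, and that such a result would be pure artefact. The documents do not support this. They give neither k nor r, and the chance exceeds one half only where final pressures vary clearly less than initial ones. Nor does the plan say that the change correlation will be read as an effect of CPAP.

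**Conclusion.** The point holds as a should-fix, not a must-fix. For a final/initial SD ratio of 1 or less, the raw-change correlation is significant in roughly 10% to 75% of studies of 29 when opening pressure has no link to final pressure given initial pressure. This rests on the plan's ρ = -0.5, normal data, a two-sided 5% test and assumed values of k and r.

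No link here means none given initial pressure. If opening and final pressure are merely uncorrelated overall while r is above 0, a conditional link does exist, and a significant adjusted result would then be correct.

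As planned, the three correlations could be read as three agreeing findings when they may express one association.

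**What to change.** In item 4, define change as final minus initial pressure and add the partial Spearman correlation of opening pressure with final pressure given initial pressure. A rank regression of final pressure on opening and initial pressure would serve equally. State that any claim about pressure response beyond baseline rests on this analysis, and that the raw-change correlation is descriptive only. Note as a caveat that measurement error in initial pressure can leave residual bias in the adjusted result.

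The cost is a few lines of text and one degree of freedom. Initial pressure is already collected, so no new data or participants are needed. The change should be made before any results are seen, because an adjustment chosen afterwards would lose its protection.

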Eustachian tube dysfunction is a poorly defined and understood clinical entity. While it is agreed upon that it is the primary etiology of chronic otitis media, particularly in adults, the exact physiology has been elusive. While many different theories have been proposed with evidence presented in addition, *Cummings* (Flint, *et al.*) describes two key physiological changes, whether it be mechanical obstruction (e.g., adenoid hypertrophy) or functional (normal anatomy with poor function). The former is likely more common in children with the latter best described in patients with cleft palate. Purely anatomical comparisons have not provided a definite etiology for why some individuals have significantly greater dysfunction.

In describing the clinical entity of Eustachian tube dysfunction, the literature varies between symptom descriptions, objective findings, and clinical outcomes (ie, need for surgery, etc.). Even when using objective findings, there is disagreement as to what degree of negative pressure on tympanometry constitutes Eustachian tube dysfunction. Attempts to measure function have been unsuccessful. A recent review by Norman, *et al.* found such significant variation in how ETD was defined in the literature that it was felt that no reasonable conclusions could be drawn regarding specific, consistent diagnostic criteria. While multiple symptom score indices have been proposed, including the Eustachian tube dysfunction questionnaire (ETDQ-7, Figure 1), they have not reached widespread use.

Figure 1. The Seven Item Eustachian Tube Dysfunction Questionnaire (ETDQ-7).

Over the past 1 month, how much has each of the following been a problem for you?	Severe Problem						
	No Problem	Moderate Problem					
1. Pressure in the ears?	1	2	3	4	5	6	7
2. Pain in the ears?	1	2	3	4	5	6	7
3. A feeling that your ears are clogged or “under water”?	1	2	3	4	5	6	7
4. Ear symptoms when you have a cold or sinusitis?	1	2	3	4	5	6	7
5. Crackling or popping sounds in the ears?	1	2	3	4	5	6	7
6. Ringing in the ears?	1	2	3	4	5	6	7
7. A feeling that your hearing is muffled?	1	2	3	4	5	6	7

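### Secondary analysis: relating ETDQ-7 to the pressures by Spearman correlation instead of t-tests/ANOVA would gain about 4–20 power points at n=29, if the relation is monotone with r of 0.3–0.7

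*Combined protocol and SAP*

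**What the plan says.** Statistical Considerations, item 4, assigns Spearman correlation to the primary analysis. It relates the CPAP pressure at which the ears pop to the "initial and final tympanometric pressure as well as the change in tympanometric pressure". Item 5 then turns to the questionnaire: "We will use t-tests and/or ANOVA to assess the relationship of the above pressures to ETDQ-7 responses". The pressures meant are the four in item 4: pop pressure, starting pressure, final pressure and their change. Item 5 names no grouping variable, number of groups or cut. Item 1 defers any grouping to the analysis stage, to be based on data gathered in the study.

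Background, Figure 1, shows the ETDQ-7 as seven questions under the stem "Over the past 1 month, how much has each of the following been a problem for you", each answered from 1 to 7. A total would run from 7×1=7 to 7×7=49. The documents do not say whether the total, the mean or single items will be analysed.

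The opening summary says in general terms that the "tests include Spearman correlations, t-tests, and Wilcoxon Rank-Sum Test". It does not tie any of these tests to ETDQ-7.

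**The concern.** A t-test or ANOVA compares means across categories. With two graded measurements there are two ways to get categories. One is to cut the score or the pressure into groups, which under item 1 would happen after the data are seen. The other is to use the seven answers to a single item as an ANOVA factor, which ignores their order. Both lose information already collected, and a real association between symptoms and pressure is then more likely to be missed. The protocol already uses a method for two graded variables in item 4, so the loss is avoidable.

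**Working it through.** **Inputs from the protocol.** n=29 and an assumed correlation of −0.500 between opening pressure and starting middle ear pressure (item 3); the tests in items 4 and 5; the 1–7 item scale (Figure 1).

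**Assumptions.** The protocol states neither alpha nor power; I take two-sided 0.05 and 80%. It gives no correlation for ETDQ-7; I take 0.3–0.7, with 0.2 and 0.8 as checks. The sign does not matter in a two-sided test.

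**Step 1: the plan's own figure.** n = ((1.960 + 0.842)/atanh(0.5))² + 3 = (2.802/0.549)² + 3 ≈ 29.01. The stated 29 is reproduced, for the primary correlation only. The usual Spearman variance factor of 1.06 gives 1.06×26.01 + 3 ≈ 30.6. This is why Spearman at n=29 and r=0.5 falls a little short of 80% below.

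**Step 2: power under a monotone relation.** For each r, 20,000 datasets of 29 were simulated as y = r·x + √(1−r²)·e, with x and e standard normal. Spearman was tested by t = r_s·√(27/(1−r_s²)). The grouped tests were a median split (14/15), a 2:1 split (19/10) and ANOVA on tertiles (10/10/9). Losses come from unrounded power, so they can differ by a point from the rounded columns.

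| r | Spearman | Near-balanced groups | Loss (points) |
|---|---|---|---|
| 0.3 | 32% | 21–24% | 9–12 |
| 0.4 | 53% | 38–40% | 14–16 |
| 0.5 | 76% | 56–59% | 16–20 |
| 0.6 | 91% | 76–79% | 12–15 |
| 0.7 | 98% | 91–94% | 4–7 |

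At r=0 every test rejected in about 5% of datasets, so the gain is not bought with false positives.

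**Step 3: sensitivity.**
- Outside the range, the gain is about 4–5 points at r=0.2 and about 1 point at r=0.8.
- With a right-skewed integer score from 7 to 49 and r=0.5, Spearman has 76%, against 56–59% with the score grouped and 56–57% with the pressure grouped.
- A 4:1 split loses 14–29 points and quartiles lose 5–21.
- Using the seven levels of one item as an ANOVA factor, with no cut, loses about 10–30 points. With equally frequent levels and r=0.5 the figures are 74.1% against 44.5%.
- At 31 or 32 participants, the protocol's enrolment and accrual figures, the gain over median and tertile groups is about 3–18 points.

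**Step 4: the same loss in participants.** At r=0.4–0.5 the near-balanced grouped tests need about 40–44 participants to match Spearman at 29, which is 11–15 more.

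**Step 5: shapes that reverse the order.**
- *Step of 1.0 SD.* With the split exactly on the step, grouping wins: 74% against 58% (step at the median) and 69% against 49% (step at the upper third). With the split misplaced it loses: 39% against 58% and 37% against 49%.
- *U-shape with pressure in tertiles.* Grouping wins: 34–97% against 8–13% when the score follows the absolute standardised pressure with weight 0.5–0.9, and 18% against 7% for a quadratic with weight 0.5.

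**Step 6: precision.** At an observed Spearman of 0.5, Fisher z = 0.549 and SE = √((1 + 0.5²/2)/26) = 0.208. The 95% interval is tanh(0.549 ± 1.96×0.208), about 0.14 to 0.74. The better test is still imprecise at this size.

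**The case against.** The strongest reply is that the advantage depends on a shape and strength that the documents do not supply. A reader might take the summary's statement "We hypothesize an inverse relationship between middle ear pressure and air pressure as delivered by CPAP" as support for a monotone relation. That theory concerns opening pressure and says nothing about symptom scores. Item 5 itself looks for a tympanometric cut point, which is a threshold idea, and a grouped test does better when there is a true step and the split falls on it. This stands, and it makes the gain conditional. It does not rescue the plan as written, because no cut is named and a misplaced split loses to Spearman even when the step is real.

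A reader might also infer that the planned tests force a cut. They do not, since the levels of one item could serve as the factor; that route loses more. Nor does the plan rule out Spearman for ETDQ-7, because the summary lists it among the tests in general. Nor does item 1 say that several cuts will be tried and the best one kept. A single median split taken from the data would satisfy it, so inflation of the false-positive rate is possible but not shown.

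Finally, this is a secondary analysis in a study of about 30 people. The sample size does not rest on it, and the primary analysis already uses Spearman.

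**Conclusion.** The point holds as a cheap improvement to a secondary analysis. Under a monotone relation with r of 0.3–0.7, n=29 and two-sided 0.05, Spearman gains about 4–20 power points over near-balanced two- or three-group tests. The gain is largest around r=0.5 and small at r=0.2 or 0.8. The shape and the correlation are my assumptions. For a U-shape or a correctly placed step, grouping would be better. A reader might go further and conclude that the study's main result is at risk; the documents do not support that, because item 4 is unaffected.

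**What to change.** In item 5, replace the t-test/ANOVA wording with: *Spearman correlations, with 95% CIs, of the ETDQ-7 total with initial and final tympanometric pressure, change in tympanometric pressure, and CPAP pop pressure, each with a scatterplot.* Group means may be shown descriptively.

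The cost is wording only: no new data, visits or participants, and all four pressures are kept. There are two downsides. There is no headline mean difference between symptom groups, and Spearman can miss a non-monotone relation, which is why the scatterplots are needed.

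A minor and separate matter is the ROC analysis in item 5, described as "using ROC curve analyses to determine if there is a true tympanometric pressure cut point to define ETD". It names no reference for who has ETD and no threshold. ETDQ-7 is the natural reading, while the summary's description of ETD by negative tympanometric pressure would be circular here. Item 3 says "The accrual goal will be 32, with an interim analysis at 16". Before that interim look, fix one reference not derived from tympanometry. An ETDQ-7 total threshold would serve, taken from the validation study in the bibliography only if that study reports one. Report the AUC and cut point as exploratory, with bootstrap confidence intervals.

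How to handle participants whose ears never pop, and which ear is analysed, are questions about the item 4 analysis. They should be raised separately and add nothing to the gain claimed here.
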